nicotine related to cigarette smoking. It contains six questions that evaluate the quantity of cigarette consumption, the compulsion to use, and dependence. Yes/No items are scored from 0 to 1 and multiple-choice items are score from 0-3. The higher the total score, the more intense the study participant's physical dependence to nicotine. For study participants that also use electronic nicotine delivery systems (ENDS) also known as electronic cigarettes, vape pens, vapes, eHookahs, JUULS, etc; their dependence will be measured using the Penn State Electronic Cigarette Dependence Index, a 10-item scale with scores ranging from 0 to 20. The higher the total score, the more intense the study participant's dependence to ENDS.

The study participant will then set a quit date in 15 days and be enrolled in the text messaging program. Study participants will either be assigned to the control group (SmokefreeTXT) or intervention group (SmokefreeSGM) through the randomization function in REDCap. Following completion of the assessment, the study participant will be sent a \$15 e-gift card via email and mailed a 6-week supply of nicotine patches. The dosage of nicotine patches will be dependent on whether the study participant identified as a light smoker (≤ 10 cigarettes/day) or a heavy smoker (smoke > 10 cigarettes/day). Light smokers will receive 3 boxes of 14 mg nicotine patches and heavy smokers will receive 3 boxes of 21 mg nicotine patches.

1-Month Assessment

Study participants will complete the 1-month assessment (Appendix F) via phone, telehealth, or in-person and be asked a series of demographic and tobacco use questions similar to the baseline screening: changes to contact information, sexual orientation and gender identity, smoking behaviors, and nicotine patch use. The research team member will conduct a FTND and/or Penn State Electronic Cigarette Dependence Index for those study participants that have not quit smoking. The research team member will also pose the question: "As an LGBTQ+ smoker, do you feel that the content of the text messages was tailored to your needs? Can you

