explain why or why not?" Following completion of the assessment, the study participant will be sent a \$15 e-gift card via email and mailed a 2- or 4-week supply of nicotine patches depending on if they identified as a light smoker (smoke \leq 10 cigarettes/day) or a heavy smoker (smoke $>$ 10 cigarettes/day) during the baseline assessment. Light smokers will receive 1 box of 7 mg nicotine patches and heavy smokers will receive 1 box of 14 mg and 1 box of 7 mg nicotine patches.

Individuals living in the Greater Houston Area will be given the opportunity to complete the 1-month assessment in-person at the University of Texas Health Science Center at Houston School of Public Health (RAS E515). In doing so, they will be able to complete an exhaled carbon monoxide (CO) test (coVita Smokerlyzer) for additional compensation (\$30 gift card) and a voucher for parking in or public transportation to the Texas Medical Center. Unlike saliva cotinine tests, which will produce positive results for individuals who both smoke traditional cigarettes and use electronic nicotine delivery systems (ENDS), the CO test will only produce elevated results for traditional cigarette smokers. Implementing this procedure will also allow us to test its feasibility before launching a larger-scale efficacy trial for the SmokefreeSGM program.

3- and 6-Month Assessments

Study participants will complete the 3- and 6-month assessments (Appendix G & H) via telehealth and will conduct the saliva cotinine test to verify their smoking status. Individuals living in the Greater Houston Area will be given the opportunity to complete these assessments in-person at the University of Texas Health Science Center at Houston School of Public Health (RAS E515). In doing so, they will be able to complete an exhaled carbon monoxide (CO) test (coVita Smokerlyzer) for additional compensation (\$30 gift card at each assessment) and a voucher for parking or public transportation to the Texas Medical Center.

Study participants will be asked a series of demographic and tobacco use questions similar to the 1-month assessment. If the saliva test results indicate that a study participant is still a smoker, a research team member will conduct a FTND and/or Penn State Electronic Cigarette Dependence Index. Following completion of the 3- and 6-month assessments, the study participant will be sent a \$20 and \$25 e-gift card via email respectively.

Semi-structured Interview

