Quantitative data collected via text messages will be downloaded from Mosio as an Excel, SPSS, R, SAS, or STATA dataset. These software packages will be used for analysis purposes. Study variables will be summarized using standard descriptive statistics. The distributional characteristics of relevant variables will be examined using box plots and histograms to ensure normality assumptions. Routine descriptive statistics, including proportions, means, and standard deviations as well as graphical methods will be reported to explore distributions for all variables.

Recruitment rates will be defined by dividing the number of SGM smokers who consent and complete the baseline assessment by the number of SGM smokers who are approached and invited to participate in the text-based program. Retention rates will be defined by dividing the

number of SGM smokers who remained in the text-based cessation program and completed the 3- and 6-month assessments by the number of SGM smokers recruited. The recruitment and retention rates will be calculated along with confidence intervals (CIs) for specific arms and combined arms.

We will use t-test/Mann-Whitney or chi-squared/Fisher's exact test to compare baseline demographic variables between SGM smokers and those who refuse to participate or drop out from the study. Smoking abstinence outcomes will be defined as 7-day smoking abstinence along with negative saliva cotinine tests. Because abstinence is a binary variable (yes, no) the primary method of analysis will be a simple post-test analysis among SGM smokers with a generalized logistic mixed model, using a random intercept to incorporate the intra-subject correlation. Important covariates that will be used to adjust for potential baseline differences include age, level of education, biological sex, gender identity/sexual orientation, race/ethnicity, marital status, working status, years smoking, nicotine dependence, use of other tobacco products, and living with other household members who smoke. Odds ratio (OR) of smoking abstinence in the intervention group (SmokefreeSGM) relative to the control group (SmokefreeTXT) will be used to estimate effect size. Using logistic regression, abstinence will be regressed onto a dummy coded SmokefreeSGM vs. SmokefreeTXT group indicator, with the exponentiated coefficient of the group indicator yielding the OR.

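### The abstinence definition makes no provision for nicotine replacement, so a quitter still using a patch at the 3-month saliva test cannot be counted as abstinent

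*Combined protocol and SAP*

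**What the plan says.** All references are to the combined protocol and SAP.

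- **Statistics:** "Smoking abstinence outcomes will be defined as 7-day smoking abstinence along with negative saliva cotinine tests". No exception or alternative marker is given for someone using nicotine replacement.
- **Baseline Assessment:** each participant is to "set a quit date in 15 days" and is "mailed a 6-week supply of nicotine patches". The contents are: "Light smokers will receive 3 boxes of 14 mg nicotine patches and heavy smokers will receive 3 boxes of 21 mg nicotine patches".
- **1-Month Assessment:** participants are then "mailed a 2- or 4-week supply of nicotine patches". "Light smokers will receive 1 box of 7 mg nicotine patches", while "heavy smokers will receive 1 box of 14 mg and 1 box of 7 mg nicotine patches". Patch use is one of the topics asked about at this visit.
- **3- and 6-Month Assessments:** these are the only follow-up visits with a saliva test. Their questions are described as similar to those at 1 month. "If the saliva test results indicate that a study participant is still a smoker", the dependence questionnaires are given.
- **Specificity of the tests:** the 1-Month Assessment section notes that cotinine is also positive in e-cigarette users, whereas exhaled carbon monoxide (CO) rises only with conventional cigarettes. CO is optional, is offered in person to Greater Houston residents, and is not part of the abstinence definition.
- **Exclusion Criteria, item 6:** current use of cessation medication is a bar at entry. Nothing is said about products obtained later.

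The document does not state the day patches are to be started, whether the 1-, 3- and 6-month visits are counted from baseline or from the quit date, or how wide the visit windows are.

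**The concern.** The verification test responds to nicotine exposure, and the trial itself supplies nicotine. The protocol draws this distinction for e-cigarettes but not for the patches it mails. That patches also raise cotinine is an inference from the same reasoning, not a statement in the protocol.

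Under the Statistics definition, a participant who has truly stopped smoking but is using a patch, or another nicotine-replacement product, at the 3-month test is coded as not abstinent. This is a rule that gives a wrong answer for an identifiable group, not merely a missing detail. Abstinence rates are a stated output of the trial. The 3-month result would also feed the logistic mixed model and the odds ratio, and a larger efficacy trial is expected to follow. With 50 participants per arm, two or three miscoded quitters visibly change a rate.

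**Working it through.** **Supply.** Six weeks in three boxes is 6 / 3 = 2 weeks per box. One further box is 2 weeks and two boxes are 4 weeks, which reproduces the protocol's second shipment. Totals are 6 + 2 = 8 weeks (56 daily patches) for light smokers and 6 + 4 = 10 weeks (70 patches) for heavy smokers.

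**End of supply.** Assume one patch a day without gaps, starting on the quit date (day 15). Last patch day = 15 + number of patches − 1:
- light: 15 + 56 − 1 = day 70
- heavy: 15 + 70 − 1 = day 84

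**Days from last patch to the 3-month test**, by what 3 months is taken to mean:

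| Visit counted as | Visit day | Light | Heavy |
|---|---|---|---|
| 12 weeks from baseline | 84 | 14 | 0 |
| 90 days from baseline | 90 | 20 | 6 |
| 90 days from quit date | 105 | 35 | 21 |

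Starting patches at baseline instead would end the heavy-smoker supply on day 69, which is 21 days before a day-90 visit.

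**Slippage needed for overlap.** If the supply is finished, each skipped day or day of late start moves the last patch one day later. Days 15 to 90 are 76 days. A heavy smoker with 70 patches reaches the test day after 76 − 70 = 6 skipped days (6/76, about 8%). A light smoker needs 76 − 56 = 20 (20/76, about 26%). With the visit counted from the quit date, a heavy smoker needs 21 of 91 days (about 23%).

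**Washout.** The document gives no cotinine cut-off or clearance time, so assume w = 2 to 7 days. With s skipped days, a heavy smoker tested on day 90 may still be positive if 90 − (84 + s) < w, that is s > 6 − w. At w = 2 this takes 5 skipped days; at w = 7 it takes none.

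**Late mailing** is a weak route. Counting from baseline, the second shipment follows a visit at about day 30, and the first supply lasts to day 56. A delay would have to exceed 56 − 30 = 26 days to push patch use later.

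**Effect on the results.** The proportion of quitters on patches at the test is not in the document, so this is illustration only. Assume true abstinence of 10% (control) and 20% (intervention): OR = (0.20/0.80) / (0.10/0.90) = 2.25.
- Equal miscoding of 10% of quitters in each arm: observed 9% and 18%, OR = (0.18/0.82) / (0.09/0.91) = 2.22.
- Equal miscoding of 30%: observed 7% and 14%, OR = (0.14/0.86) / (0.07/0.93) = 2.16.
- 10% in control, 30% in intervention: observed 9% and 14%, OR = (0.14/0.86) / (0.09/0.91) = 1.65.
- 30% in control, 10% in intervention: observed 7% and 18%, OR = (0.18/0.82) / (0.07/0.93) = 2.92.

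Equal miscoding lowers both rates and hardly moves the odds ratio. Unequal miscoding moves it in either direction.

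**The case against.** The strongest reply is that the supply is designed to run out before the test. Used on schedule it does so for any calendar 3-month visit, and with a quit-date origin the margins of 21 and 35 days exceed any washout in the assumed range. Participation of about 8 months is compatible with that origin. This stands: a reader might infer that the shipments themselves place quitters on patches at 3 months, and the document does not support that. What remains is that the origin is unstated, and one plausible origin leaves heavy smokers 6 days or none.

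A reader might also take the sentence about a saliva result showing that someone is still a smoker as a coding rule for every positive test. It only triggers the dependence questionnaires; the outcome is governed by the Statistics section.

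Patch use may already be asked at 3 and 6 months, since the questions are said to resemble those at 1 month. The forms (Appendices G and H) are not reproduced, so it cannot be said that a date of last use is missing. This too stands, and it makes the remedy smaller.

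Finally, the Background criticises earlier studies for relying on unverified quit reports. Replacing the cotinine rule by self-report for patch users would weaken the very feature the trial values. That is a good reason to keep the strict definition. It is not a reason to leave patch users without a prespecified second analysis.

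**Conclusion.** The gap is real and conditional. A quitter using a patch or other nicotine replacement at the 3-month test cannot meet the definition. Reaching that state requires skipped days, a late start, a 12-week visit counted from baseline (heavy smokers), or non-study nicotine replacement. For heavy smokers the margin is 6 days with a 90-day visit from baseline and 21 days from the quit date, assuming daily use from day 15.

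The likely consequence is some under-counting of 3-month abstinence in both arms; its frequency cannot be computed from the document. A reader might infer a bias against the tailored arm. Nothing supports that: both arms receive the same supply, and the odds ratio is materially affected only if patch use at the test differs by arm, in a direction that cannot be known beforehand. Nor does on-schedule use of the trial's patches explain a positive test at 6 months, although later non-study products could.

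Because the objective is feasibility and acceptability and no power claim is made, this is a should-fix point, not a must-fix one.

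**What to change.** 1. At 3 and 6 months, before the saliva test, record the date of last use of a patch or other nicotine-replacement product. If the forms already ask about patch use, this adds only the date and the other products.
2. In the Statistics section, keep the cotinine-negative definition and prespecify a second analysis by arm. In it, a participant who reports 7-day abstinence, tests cotinine-positive and used nicotine replacement in the previous 7 days is not classed as smoking on cotinine alone. Use the CO result where there is one; otherwise report the person as self-reported abstinent on nicotine replacement. Present both abstinence rates and both odds ratios. Fix the rule before outcomes are analysed.
3. State the origin and window of the 1-, 3- and 6-month visits as they are actually run.

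No change to patch dose, supply or shipment timing is proposed. Item 3 asks for the visit timing to be stated, not moved: re-timing visits to the quit date could delay the second shipment, which follows the 1-month visit.

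The cost is one question, a few sentences in the Statistics section and a visit-timing statement. The downside is that some abstainers in the second analysis rest on self-report; the strict analysis gives the lower bound on the abstinence rates.

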- 4) Pregnant or breastfeeding persons (nicotine patches are not generally recommended to this groups since nicotine can affect fetal and neonatal brain development)
- 5) Contraindication for nicotine patches. Absolute contraindications include: severe eczema

or serious skin conditions, allergy to nicotine patches, pregnancy, breastfeeding, heart attack in the past 2 months, ongoing angina, peptic ulcer disease, arrhythmia, or uncontrolled blood pressure. Potential contraindications include: stroke in the past 6 months, insulin therapy, and a current diagnosis of liver, kidney, or heart disease. Study participants reporting a potential contraindication will require approval from their primary care provider and/or other treating physician (e.g., psychiatrist) to use nicotine patches. If the request is denied or not returned in 2 weeks, potential study participants will be excluded from the study.

- 6) Current use of tobacco cessation medications
- 7) Enrollment in another smoking cessation study
- 8) Non-English speakers

Study Procedures.

Recruitment Procedures

Active efforts will be made to identify subjects who are suitable for enrollment into this part of the study. Flyers (Appendix B) offering help to SGM individuals interested in quitting smoking will be distributed at local community organizations and health care facilities working for SGM groups. We will also advertise through the Health Equity Research Group's (HERG) social media accounts (i.e., Twitter and Facebook).

Screening Part A and B

Interested individuals will contact the research team. The screening process will take place over the phone, through telehealth (i.e., Microsoft Teams, Webex, or Zoom), or in-person, and will be divided into two parts. Part A of the screening will collect demographic information in addition to an assessment of the inclusion and exclusion criteria (Appendix C). Study participants who are

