This is a minimal risk study. The risks of using either text-based platforms, completing the 1-, 3-, and 6-month assessments, and participating in the structured interview are minimal and may result in: (1) emotional discomfort due to discussion about sensitive issues, and (2) breach of confidentiality. Distress will be minimized by assuring study participants that they do not have to respond to texts and/or answer any questions during the assessments and the one-time individual interview that they do not feel comfortable answering and may withdraw from the study at any time without repercussion. Confidentiality will be maintained by numerically coding all data and password-protecting computer files. Data will be stored on a secure server with a firewall to protect the data and to prevent unauthorized access. Data on the server will also be password protected and only accessible to research team members who have met UTHealth IRB's requirements for training in Human Subjects' Protection. All study participants will be

assigned a unique identification code that will be stored separately from identifying information. All electronic datasets will be saved in the institutional shared drive and only research team members will be able to access them. The text messaging program will be implemented by the vendor, Mosio. Mosio is hosted by Lightcrest, an established, trusted vendor with documented security and regulatory compliance through Equinix. For data protection redundancy, backups are hosted using AWS HIPAA eligible services in a geo-diverse location. All production and backup data centers are located within the United States.

For study participants that complete the exhaled carbon monoxide test (coVita Smokerlyzer) during the 1-, 3- and 6-month assessments, the device mouth pieces will be disposed of directly after use. No biological samples will be taken from the study participant. Results will be recorded from the device into the corresponding REDCap form. Additionally, the devices will be appropriately cleaned and disinfected before and after each use.

STATISTICS

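### The second nicotine patch shipment follows completion of the 1-month assessment; the protocol body states no prior check for patch reactions or contraindications new since entry

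*Combined protocol and SAP*

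**What the plan says.** All references are to the combined protocol and SAP.

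- **Entry (Exclusion Criteria, items 4 and 5).** Pregnancy and breastfeeding exclude, with an explanation based on fetal and neonatal harm. The absolute contraindications include "allergy to nicotine patches, pregnancy, breastfeeding, heart attack in the past 2 months, ongoing angina, peptic ulcer disease, arrhythmia, or uncontrolled blood pressure". A second tier needs a treating physician's agreement: "Potential contraindications include: stroke in the past 6 months, insulin therapy, and a current diagnosis of liver, kidney, or heart disease". The default there is cautious: "If the request is denied or not returned in 2 weeks, potential study participants will be excluded from the study".
- **First shipment (Baseline Assessment).** A 6-week supply is mailed: "Light smokers will receive 3 boxes of 14 mg nicotine patches and heavy smokers will receive 3 boxes of 21 mg nicotine patches".
- **1-month contact (1-Month Assessment).** The listed topics are "changes to contact information, sexual orientation and gender identity, smoking behaviors, and nicotine patch use". A dependence scale for those who have not quit and a question on message tailoring follow.
- **Second shipment (1-Month Assessment).** On completing the assessment the participant is "mailed a 2- or 4-week supply of nicotine patches depending on if they identified as a light smoker" or a heavy smoker at baseline. The boxes step the dose down: "Light smokers will receive 1 box of 7 mg nicotine patches and heavy smokers will receive 1 box of 14 mg", plus one of 7 mg for the heavy group.
- **Risk (Data Safety and Monitoring).** "The risks of using either text-based platforms, completing the 1-, 3-, and 6-month assessments, and participating in the structured interview are minimal"; the two risks then named are emotional discomfort and loss of confidentiality. Patches are not mentioned.

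**The concern.** The protocol treats nicotine patches at entry as a product that some people should not receive and that others should receive only with medical agreement. Several of the listed conditions can begin after entry, such as pregnancy, angina, arrhythmia or the start of insulin therapy. Patch allergy is a special case: someone who has never worn a patch may learn of it only from the first supply. The 1-month assessment is the first scheduled assessment after that supply is mailed, so it is the natural place to look again. The body does not say that staff do so, or what they should do if a participant reports a problem.

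What is at stake is participant protection. Read literally, the shipping rule sends more patches to a person whom the same protocol would have turned away at the door.

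**Working it through.** The point rests on setting the sections side by side. The arithmetic only places the 1-month contact within the supply and the calendar.

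**1. Is a repeat check stated anywhere in the body?**

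| Section | What it provides | Repeat check before the second shipment? |
|---|---|---|
| Exclusion Criteria 4 and 5 | Screening and physician approval | At entry only |
| 1-Month Assessment, topics | Patch use among the topics | Reactions, pregnancy and health changes not listed |
| 1-Month Assessment, shipment | Trigger is completion; content follows baseline category | No condition stated |
| Data Safety and Monitoring | Two non-patch risks; right to withdraw at any time | None |
| Ethics | Minimal-risk statement | None |
| Quality Control and Assurance | Forms checked to confirm that entry criteria were respected; staff available for questions | Checks the criteria were met; does not say they are asked again |

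**2. Do the supply figures agree?** Three boxes for 6 weeks give 6 / 3 = 2 weeks, or 14 daily patches, per box. One box is then 2 weeks (light) and two boxes 4 weeks (heavy), which matches the stated 2- or 4-week supply. The total is 6 + 2 = 8 weeks (56 days) for light smokers and 6 + 4 = 10 weeks (70 days) for heavy smokers.

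**3. What is still in hand at 1 month?** Assumptions, none stated in the protocol: patches start on the quit date (day 15), one is used per day, and a month is 30 days. The first supply is 42 days.
- Month counted from baseline: 42 − (30 − 15) = 27 days left.
- Month counted from the quit date: 42 − (45 − 15) = 12 days left.

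Either way the participant still holds patches, so withholding the new box does not by itself end exposure. Advice on patches in hand is needed too.

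**4. What would a hold cost?** With a 2-week wait for a physician, as at entry, the margin is 27 − 14 = 13 days in the first case. In the second it is 12 − 14 = −2, a gap of about 2 days plus mailing time.

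**5. Would a later question protect anyone?** On the same assumptions the planned supply ends on day 15 + 56 − 1 = 70 (light) or 15 + 70 − 1 = 84 (heavy). The 3-month contact falls at about day 91 or later. A question there records past events but cannot prevent exposure from the planned supply.

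**6. Can the change still reach this trial?** The summary gives a study end of December 2023 and participation of about 8 months. If that end applies to the last participant, 31 December 2023 less 8 months is about 30 April 2023 for the last enrolment. The last 1-month contacts then fall on 30 May (30 days later) to 14 June 2023 (45 days later), before this version of 25 July 2023. The screening section still describes enrolment as being sought, so the actual status is unknown.

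**The case against.** The strongest reply is that the body only summarises the 1-month form. Appendix F is not in the supplied text, and patch use is among its topics, which is a natural opening for a report of a reaction. The consent form (Appendix D) may state the patch risks. The assessment is itself a contact with staff trained in good clinical practice, staff are available by phone, email or telehealth, and participants may withdraw at any time. Entry screening is detailed, and the second shipment steps the dose down. Nothing tells staff to mail patches in the face of a disclosed contraindication.

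Most of this stands, and it limits the point. A reader might infer that no safety check is made in practice, or that staff would knowingly send patches to a pregnant participant. The documents do not support either reading: the forms are unseen, and a rule that is silent about a hold is not an instruction to ignore a disclosure.

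What survives is narrower. The routes named depend on the participant volunteering the problem. Even if Appendix F asks the right questions, the body does not make shipment depend on the answers or say who may hold the box.

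**Conclusion.** The point holds for the protocol body, at minor severity. The second shipment is tied to completing the 1-month assessment and to the baseline smoking category. No check for reactions or new contraindications is stated, although the protocol's own entry criteria treat these as reasons to exclude or to seek approval. This is more than missing detail, because closing the gap changes what staff do at an existing contact.

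Its size cannot be put in numbers. The documents give no rate of new contraindications or patch reactions. The ceiling is the 100 participants planned, and the number affected is probably small, which is a judgement. The days-in-hand figures show where the 1-month contact sits in the supply; they measure neither frequency nor harm.

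A reader might also infer a bias in the abstinence comparison. The documents do not support that: the patch rules are the same in both arms, so the missing check leaves the between-arm comparison unaffected.

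**What to change.** Amend the 1-Month Assessment section so that, at the existing contact and before shipping, staff ask about patch reactions and re-ask exclusion criteria 4 and 5. Then:

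- **Absolute contraindication or significant reaction:** withhold the shipment, advise the participant to stop the patches in hand, and notify the investigator.
- **New potential contraindication:** hold the shipment until a treating physician approves, as at entry. The investigator decides whether patches in hand are paused meanwhile.
- **Neither:** ship as planned.

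If Appendix F already asks these items, cite it and add only the stop and hold rule. Name the role that applies the rule, since the summary lists no co-investigators or coordinator. A 3-month question is not needed as a safeguard, because the planned supply would be finished by then.

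The cost is a short amendment, a few questions at a contact that already takes place, some clinical judgement, and some delayed or withheld boxes, with a possible short gap in supply during a hold. The change does not reach people who miss the 1-month contact; they get no second shipment but keep the first supply. If enrolment had already closed by this version, the benefit falls mainly to the larger efficacy trial that the protocol mentions.
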